7.1.2 Treatment period

The treatment period commences on the first day of the first cycle (C1D1) of LEE011 and ends after the last dose of LEE011.

Patients who enter the study will be treated with daily dosing of oral LEE011 for 21 consecutive days followed by a 7 day planned break until the patient experiences unacceptable toxicity that precludes any further treatment, disease progression, and/or treatment is discontinued at the discretion of the investigator or by patient's premature withdrawal.

During the study treatment period, patients will be regularly monitored to assess the safety and early anti-tumor activity of the treatment. For the purpose of scheduling and evaluations, a treatment cycle will consist of 28 days.

For details of assessments during the treatment period, refer to [Table 7-1](#).

7.1.3 End of treatment (EOT) visit

At any time, patients may voluntarily withdraw from the study or be removed from it at the discretion of the investigator. If withdrawal occurs, or if the patient fails to return for visits, effectively withdrawing, the investigator must determine the primary reason for a patient's premature withdrawal, record this information on the End of Treatment eCRF, and notify Novartis. Patients may be withdrawn from study treatment for one of the following reasons:

1. Adverse event(s)
2. Disease progression
3. Protocol violation/deviation
4. Patient withdrew consent
5. Lost to follow-up
6. Death
7. Transfer to another Novartis clinical study that continues to provide LEE011.

Patients who discontinue study treatment for any of the above reasons (except death) should be scheduled for an EOT visit within 14 days of permanently discontinuing LEE011 at which time all of the assessments listed for the EOT visit will be performed. An EOT eCRF will be completed, giving the date and reason for stopping the study treatment.

The EOT completion evaluations are outlined in [Table 7-1](#).

All patients who discontinue study treatment, including those who refuse to return for a final visit, should be contacted 30 days after discontinuing study drug for safety evaluations and a list of antineoplastic therapies received since discontinuation. See [Section 7.1.4](#). A Study Evaluation Completion (SEC) eCRF will then be completed, giving the date and reason for study discontinuation.

[figure not shown]
For patients who refuse to return for visits or are unable to do so, every effort should be made to contact them or a knowledgeable informant by telephone. Patients lost to follow up should be recorded as such on the SEC eCRF. A patient is considered "lost-to-follow up" if the patient fails to show up for a scheduled follow-up visit and no response despite at least 3 documented failed attempts to contact the patient, such as via phone calls and/or registered letters. The investigator should show "due diligence" by documenting in the source documents steps taken to contact the patient, e.g. dates of telephone calls, registered letters, etc.

Patients that transition into the rollover clinical trial will perform end of treatment procedures. However, follow-up for safety, survival and disease progression will not be performed.

7.1.3.1 Patient replacement

Escalation part:

Patients will not be replaced on study. However, if a patient is considered as non-evaluable for the DDS, enrollment of a new patient to the current cohort will be considered if there is less than the required number of evaluable patients. Minimum and maximum numbers of evaluable patients per cohort are defined in [Section 6.2.2](#).

Expansion part:

Patients will not be replaced.

7.1.4 Follow-up period

All patients will have safety evaluations completed 30 days after the last dose of LEE011. At this time AE, SAE and concomitant medications (including subsequent antineoplastic therapy) information during the follow-up period will be recorded on the AE eCRF and Novartis will be informed as necessary. For eCRF purposes, this will be referred to a Study Evaluation Completion (SEC).

Patients lost to follow-up should have this documented on the appropriate eCRF and attempts made to contact the patient to ascertain the reason and required study information, as described in [Section 7.1.3](#).

7.2 Assessment types

7.2.1 Efficacy assessments

[figure not shown]
All patients will have disease response assessment per RECIST v1.1 ([Appendix 1](#)). Patients with primary CNS tumors (including MRT) will have response assessment per RANO criteria ([Appendix 3](#)) whenever possible, in addition to RECIST. Disease response in neuroblastoma patients will be assessed per INRC ([Appendix 2](#)) whenever possible in addition to RECIST. Response assessments for patients with MIBG-positive disease and bone marrow-positive disease will also be done when applicable, per standard institutional practice. Disease response and progression will be determined locally by the investigator. All imaging procedures at screening must be completed within 28 days of the first dose of LEE011.

For patients with primary CNS (including MRT), the method of measurement should follow the neuro-oncology criteria of tumor response using 2-dimensional and volumetric measurements (if available) on gadolinium chelate-enhanced brain tumor magnetic resonance imaging (Gd-MRI) ([Appendix 3](#)). All Gd-MRIs (standard brain tumor magnetic resonance imaging [MRI] including both pre-contrast and post-contrast images using a Gadolinium (Gd) chelate as the contrast agent) should be performed when the patient is on a non-increasing dose of corticosteroids for at least 7 days.

For patients with non-CNS tumors, the method of measurement should follow standard practice (ie, computed tomography [CT] or MRI scans) and response will be assessed using Response Evaluation Criteria in Solid Tumors (RECIST) version 1.1 ([Appendix 1](#)). Patients with neuroblastoma will undergo MIBG scanning, and bone marrow aspirate and/or biopsy for presence of disease per standard institutional practice at screening. The use of ¹²³I for MIBG imaging is recommended for all scans. MIBG scans and bone marrow aspirates and/or biopsies should be performed within 28 days of the first dose of LEE011. Visible skin lesions and easily palpable subcutaneous tumors may be measured by physical examination using a ruler or calipers. Ultrasound should not be used to measure tumor lesions.

Each lesion that is measured at baseline (screening), must be measured by the same method throughout the study so that the comparison is consistent.

Antitumor activity in patients with non-measurable disease will only be noted.

Subsequent tumor evaluations will be performed on Day 22 (± 7 days) of cycles 2, 4 and 6. After cycle 6 tumor evaluations will be performed on Day 22 (± 7 days) of every 4th cycle (e.g., C10, C14, C18), or sooner if there is clinical evidence of disease progression. Tumor evaluations will also be performed at EOT. If the last prior tumor evaluation was within 28 days of EOT or objective evidence of progressive disease has already been documented, then tumor evaluations do not need to be repeated at EOT.

Tumor evaluations after the screening assessment will include evaluation of all sites of disease identified at baseline, using the same technique that was used at screening. If there was no evidence of disease in a body region at screening, that region does not need to be imaged at subsequent assessments, unless there is clinical concern for a new lesion in that body region. Bone marrow aspirate and/or biopsies and MIBG scans are not required after baseline if they were negative at screening.

The CSF test is required for primary CNS tumors (including MRT) patients at screening and is performed per institutional standards. If sampling is not feasible, patients may still enroll in study after discussion with Novartis and the investigator. Information will be collected if performed. CSF will be performed at Screening and if positive at screening, subsequent measurements are performed only for confirmation of CR as needed on Day 22 (± 7 days) of cycles 2, 4 and 6. After cycle 6 tumor evaluations, CSF test will be performed as needed on Day 22 (± 7 days) of every 4th cycle (e.g., C10, C14, C18), or sooner if there is clinical evidence of disease progression. Only 2 negative sequential CSF cytology are required for establishing CR.

All radiological assessments obtained for all patients enrolled during the study will be centrally collected and subjected to quality checks by an imaging CRO selected by Novartis. The site manual provided by the designated imaging CRO will provide further details regarding image collection.

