7.1 Study flow and visit schedule

Table 7-1 lists all of the assessments and indicates with an “X”, the visits when they are performed.

For all visits, there is a ± 3 days window on assessments to take into account scheduling over public or religious holidays if not explicitly specified otherwise. All data obtained from these assessments must be supported in the patient’s source documentation. Laboratory assessments that were completed within 72 hours prior to Cycle 1, Day 1 (C1D1) do not need to be repeated.

[figure not shown]

Table 7-1 Visit evaluation schedule

Visit Name	Protocol Section	Screening	Treatment Period													EOT	SEC	
			Cycle 1						Cycle 2			Cycles 3-6			Subsequent cycles			
			1	2	3	4	5	6	7	8	9	10	11	12...	22			23...
Day of Cycle		-21 to -1	1	2	8	15	22	1	15	22	1	15	22	1	22	Last	30 day follow-up	
Obtain Main Informed Consent	7.1.1.	X																
Patient History																		
Demography	7.1.1.3.	X																
Inclusion/exclusion criteria	5.2/5.3.	X																
Medical History	7.1.1.3.	X																
Prior Antineoplastic therapies	7.1.1.3.	X																
Diagnosis and extent of cancer	7.1.1.3.	X																
Prior/concomitant medications	6.4.	Continuous																
Physical examination	7.2.2.1.	X	X		X	X	X	X	X		X	X		X		X		
Performance status	7.2.2.4.	X	X					X			X			X		X		
Height, Weight, BSA	7.2.2.3.	X	X					X			X			X		X		
Vital signs	7.2.2.2.	X	X		X	X	X	X	X		X	X		X		X		
Laboratory assessments	7.2.2.5.																	
Hematology	7.2.2.5.1.	X	X		X	X	X	X	X		X	X		X		X		
Chemistry	7.2.2.5.2.	X	X		X	X	X	X	X		X	X		X		X		
Thyroid	7.2.2.5.3.	X						X			C4,			C8,		X		

Visit Name	Protocol Section	Screening	Treatment Period														EOT	SEC			
			Cycle 1						Cycle 2			Cycles 3-6			Subsequent cycles						
			1	2	3	4	5	6	7	8	9	10	11	12...	22	23...			777	778	
Day of Cycle		-21 to -1	1	2	8	15	22	1	15	22				1	15	22	1	22	Last	30 day follow-up	
														C6			C10,C12, etc.				
Pregnancy test	7.2.2.5.4.	X																		X	
Cardiac																					
ECHO	7.2.2.5.6.	X																		X	
ECG	7.2.2.5.5.	X	X		X	X	X	X	X					X						X	
Efficacy assessments																					
Tumor evaluation	7.2.1.	X ^a								X							C4, C6		C10, C14, C18, etc.	X	
MIBG imaging (neuroblastoma only)	7.2.1.	X ^a								If positive at Screening							If positive at Screening C4, C6		If positive at Screening C10, C14, C18, etc.	X	

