BMA and/or Biopsy (neuroblastoma only)	7.2.1.	X ^a								If positive at Screening							If positive at Screening C4, C6		If positive at Screening C10, C14, C18, etc.	X	
CSF Cytology ^b	7.2.1.	X ^a								If positive at Screening only to confirm CR							If positive at Screening C4, C6 to confirm CR		If positive at Screening C10, C14, C18, etc. to confirm CR		
Safety																					
Adverse events	8.1.	Continuous																			
Predictive and Pharmacodynamic	7.2.4.																				

Visit Name	Protocol Section	Screening	Treatment Period														EOT	SEC
			Cycle 1						Cycle 2			Cycles 3-6			Subsequent cycles			
			1	2	3	4	5	6	7	8	9	10	11	12...	22	23...		
Day of Cycle		-21 to -1	1	2	8	15	22	1	15	22	1	15	22	1	22	Last	30 day follow-up	
Biomarkers																		
Collection of archival tumor blocks/slides	7.2.4.1.	X																
BMA and/or Biopsy (neuroblastoma only) ^a	7.2.4.2.	X								If positive at Screening			If positive at Screening C4, C6		If positive at Screening C10, C14, C18, etc.			
LEE011 administration	6.1.2.		Days 1-21					Days 1-21			Days 1-21			Days 1-21				
PK blood sampling ^c	7.2.3.		X	X ^d	X	X	X	X			C3							
CSF for PK ^b	7.2.3.2.		if available when collected for efficacy assessment or routine/ standard clinical purposes															
Antineoplastic therapies since discontinuation of study treatment	7.1.4.															X	X	

^a Screening window = -28 to -1 day(s) prior to first dose of LEE011
^b only for primary CNS (including MRT)
^c An additional PK blood sample will be required if a patient has CSF collected (see Section 7.2.3.2).
^d escalation only, C1D2

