7.2.2.5.4 Pregnancy assessments

When effective contraception is required pregnancy testing is required at screening and at the end of the trial. At screening a serum pregnancy test should be performed, while at the end of trial urinary pregnancy tests are sufficient.

Pregnancy test to be performed:

- Screening (serum)
- End of treatment (urine or serum)

A positive pregnancy test is cause for immediate withdrawal.

For females to be considered “of non-childbearing potential”, patient should meet one of the following:

- Prior to onset of menarche (pre-menarche)
- Surgically sterile for at least 6 months (hysterectomy with bilateral oophorectomy or tubal ligation). Documentation of sterilization method must be provided. The date of sterilization will be recorded.

To ensure patient safety, each pregnancy in a patient on study drug must be reported to Novartis within 24 hours of learning of its occurrence. The pregnancy should be followed up to determine outcome, including spontaneous or voluntary termination, details of the birth, and the presence or absence of any birth defects, congenital abnormalities, or maternal and/or newborn complications.

Pregnancy should be recorded on a Clinical Trial Pregnancy Form and reported by the investigator to the local Novartis Drug Safety and Epidemiology (DS&E) follow-up should be recorded on the same form and should include an assessment of the possible relationship to

the Novartis study drug of any pregnancy outcome. Any SAE experienced during pregnancy must be reported on the SAE Report Form.

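### Table 7-1 gives MIBG imaging and efficacy marrow sampling an unconditional X at end of treatment, although Section 7.2.1 exempts patients who were negative at screening (low severity)

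*Protocol*

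**What the plan says.** Protocol Section 7.2.1 sets the rule for patients who screen negative: "Bone marrow aspirate and/or biopsies and MIBG scans are not required after baseline if they were negative at screening". It makes no exception for EOT. Section 4.1 points the same way, since it ties repeat marrow evaluation to patients whose marrow was involved at study entry.

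In the efficacy block of Table 7-1, the rows that begin "MIBG imaging (neuroblastoma only" and "BMA and/or Biopsy (neuroblastoma only" both cite Section 7.2.1. Their on-treatment cells are conditional. The last one in each row, for example, reads "If positive at Screening C10, C14, C18, etc". The EOT cell that follows is an X with no condition. The only footnote attached to cells in these rows concerns the screening window.

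Section 7.1.3 gives the EOT column its force. Patients who discontinue are to have an EOT visit "at which time all of the assessments listed for the EOT visit will be performed". The same section adds: "Patients that transition into the rollover clinical trial will perform end of treatment procedures".

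Section 7.2.1 also contains a general waiver. Tumor evaluations need not be repeated at EOT if the last one was within 28 days or if progression has already been documented.

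**The concern.** These two rows print the screening condition at every on-treatment visit and drop it only at EOT. A coordinator could reasonably take the change as deliberate and conclude that everyone is tested once more on leaving. For a child whose marrow or MIBG was negative at screening, that means an invasive procedure or a scan that the protocol text does not require.

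Sites would also be exposed to inconsistent handling. One that correctly follows 7.2.1 could be queried against the table, and Section 12 allows no authorized deviations. What is at stake is patient burden and consistency between sites. The dose decision and the RECIST analyses are not at stake.

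**Working it through.** No plan figure is there to reproduce. The check is a comparison of the table with the text, followed by an attempt to bound the number of patients.

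**Cells in Table 7-1**

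| Row (section cited) | On-treatment cells with the screening condition | EOT cell |
|---|---|---|
| MIBG imaging (7.2.1) | 3 of 3 | X, no condition |
| Efficacy marrow aspirate/biopsy (7.2.1) | 3 of 3 | X, no condition |

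The on-treatment cells are Cycle 2, Cycles 3-6 and subsequent cycles. In total, 3 + 3 = 6 of 6 on-treatment cells are conditional and 0 of 2 EOT cells are.

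**Is it a reading error in the extracted table?** Probably not. The tumor evaluation row has the same layout, with an X at EOT and nothing at the 30-day follow-up, and 7.2.1 separately confirms an EOT tumor evaluation.

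**Who is exposed?** There are two ways to read the 7.2.1 waiver.

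1. *It covers MIBG and marrow, with the 28 days counted from the last tumor evaluation.* The exposed group is then screen-negative neuroblastoma patients who stop without documented progression and more than 28 days after that evaluation. The schedule makes this possible:
   - From Cycle 2 to Cycle 6, evaluations fall every second cycle: 2 × 28 = 56 days apart, of which 56 − 28 = 28 days lie outside the waiver.
   - After Cycle 6, they fall every fourth cycle: 4 × 28 = 112 days apart, of which 112 − 28 = 84 days lie outside it.
   - These are nominal intervals, before the ±7-day window.

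   A patient who transfers to the rollover study while progression-free can fall in those gaps.

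2. *It covers only the row named tumor evaluation, or it is applied test by test.* If it covers only that row, it gives no relief here. If it is applied test by test, documented progression still exempts a patient, but the 28-day limb rarely does, because a screen-negative patient has no scheduled MIBG or marrow after screening.

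On neither reading does the waiver depend on the screening result, so it does not supply the missing condition.

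**How many patients?** Per patient, the excess is at most 1 marrow procedure + 1 MIBG scan = 2, each only if that test was negative at screening. The total cannot be derived:
- Section 4.1 plans about 28 patients in escalation and about 18 in the neuroblastoma expansion arm, and 28 + 18 = 46.
- Section 10.8 says the 18 include neuroblastoma patients already treated at the MTD/RDE in escalation, so the sum may count some patients twice.
- Escalation also took MRT and other tumors.
- The documents give neither the neuroblastoma share in escalation nor the screen-negative share for either test.
- SAP Section 4 reports halted enrollment and analyses of the escalation part only, so the expansion figure may not apply at all.

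**The case against.** The strongest reply is that the protocol already answers the question. Both rows name 7.2.1 as their governing section, EOT is after baseline, and 7.2.1 leaves no gap. Other EOT X's in the same table are plainly shorthand. The pregnancy test has a bare X, yet its section limits it: "When effective contraception is required pregnancy testing is required at screening and at the end of the trial". Tumor evaluation has a bare X too, and 7.2.1 waives it in stated cases. On that view, Section 7.1.3 cannot mean that every patient has every listed test.

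Most of this stands, and it is why the point is small. A reader might infer that the protocol mandates marrow and MIBG at EOT for all neuroblastoma patients. The documents do not support that, because the section the rows cite says otherwise. What survives is narrower. These two rows do not use shorthand: they spell out the condition at every on-treatment visit and omit it at one.

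A reader might also infer a drafting slip from two other screening-conditioned rows with a blank EOT cell. That comparison carries little weight. After screening, CSF cytology serves only to confirm complete response, as its last on-treatment cell shows ("If positive at Screening C10, C14, C18, etc. to confirm CR"). The biomarker marrow row follows Table 7-6, which schedules no EOT sample. Each blank has its own explanation.

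Finally, 46 might be taken as the number of patients at risk. It is not even a reliable ceiling, given the overlap described in Section 10.8.

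**Conclusion.** The conflict is real but of low severity. Two EOT cells in Table 7-1 omit a condition that 7.2.1 imposes and that the same rows print elsewhere. A site following the table could do an unneeded marrow procedure or MIBG scan in a screen-negative neuroblastoma patient, at most one of each. If the waiver in 7.2.1 extends to these tests, the group shrinks to those stopping without documented progression and more than 28 days after their last evaluation, such as some rollover patients.

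The number affected is unknown, and no instance of an unneeded test is shown. DLT and RECIST endpoints are untouched: DLTs are Cycle 1 toxicities, and RECIST response does not depend on routine EOT marrow or MIBG in patients negative on those tests. The conclusion assumes that the extracted column alignment of Table 7-1 is faithful, which the neighbouring tumor evaluation row supports.

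**What to change.** In Table 7-1, change the EOT cells of the MIBG imaging row and the efficacy marrow row from X to *If positive at Screening (see 7.2.1)*. Judge each test on its own screening result, so that a patient positive on MIBG but negative in marrow has only the MIBG at EOT. Leave 7.2.1 unchanged. The new cell text adds no trigger beyond that rule, and the cross-reference points sites to the waiver.

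The cost is two table cells in the next amendment, with no analysis change. Screen-positive patients are still scheduled for EOT testing as now. No scheduled pharmacodynamic sample is lost, because the biomarker marrow row has no EOT entry. What goes is a routine EOT check in screen-negative patients, which 7.2.1 already does not require.

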7.2.2 Safety and tolerability

[figure not shown]
Safety and tolerability assessments will include adverse event reporting and changes from baseline in laboratory measures and vital signs. Tolerability will be assessed by the incidence of AEs leading to study drug delay or discontinuation. For details on AE collection and reporting, refer to [Section 8](#).

7.2.2.1 Physical examination

A full physical examination (PE) that evaluates all major organ systems will be performed at screening. This should include a complete neurological exam. Subsequent PEs should be focused on sites of disease, and clinical signs and symptoms. Patients with CNS disease and baseline neurologic findings should have a complete neurologic exam performed at all subsequent visits.

Significant findings that were present prior to the signing of informed consent must be included in the Relevant Medical History/Current Medical Conditions page on the patient's eCRF. Significant new findings that begin or worsen after informed consent must be recorded on the Adverse Event page of the patient's eCRF.

PEs to be performed are outlined in [Table 7-1](#).

7.2.2.2 Vital signs

Vital signs (heart rate, blood pressure and temperature) will be obtained in the same position, either sitting or supine, as appropriate prior to any blood collection.

Vital signs to be obtained are outlined in [Table 7-1](#).

7.2.2.3 Height, weight and body surface area (BSA)

Height in centimeters (cm) and body weight (to the nearest 0.1 kilogram [kg] in indoor clothing, but without shoes) will be measured. Sitting height should be measured when appropriate. BSA will be measured using the patient's weight and height, in accordance with local site procedure. For the purpose of BSA calculations and potential dose readjustment at subsequent cycles, it is acceptable for the BSA to be calculated up to 7 days in advance of Day 1.

Assessments to be obtained are outlined in [Table 7-1](#).

